7.2.3 End-of-treatment Visit

For subjects who discontinue investigational product, the EOT visit should occur as soon as possible (within 14 days) after the last dose of investigational product.

7.2.4 Safety Follow-up Visit

The SFU visit should occur approximately 30 (+7) days after the last dose of AMG 510 or before any new anticancer treatment is started.

7.2.5 Long-term Follow-up

Following the SFU visit, there will be an LTFU period **during which data will be collected on the subjects' health condition, disease status, and subsequent anticancer treatment.**

Also, for subjects who discontinued study treatment without confirmed disease progression or start of subsequent anticancer treatment, tumor assessments will continue during LTFU every 12 weeks (\pm 2 weeks) for up to 3 years after last subject enrolled or until confirmed disease progression, start of subsequent anticancer treatment, death, withdrawal of consent, loss to follow-up, or end of study.

Subjects who had confirmed disease progression or started subsequent anticancer treatment, will be followed via telephone every 12 weeks (\pm 2 weeks) for assessment of survival and documentation of anticancer treatment. Subjects will be followed for up to 3 years after last subject enrolled or until withdrawal of consent, **loss to follow-up, or subject death, whichever occurs first.**

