^f **For women of childbearing potential only (defined in Criterion 215 in Section 4.2).**

^g AMG 510 will be administered daily on a repeated basis with no planned off treatment days. AMG 510 must be administered in the fasted state (no food or liquids, except water, 2 hours before to 1 hour after dosing).

^h Radiological imaging and tumor assessments are required at screening and every 6 ± 1 weeks. After **four** 6-week response assessments, radiological imaging and tumor assessment frequency will be performed every 12 ± 1 weeks until disease progression, start of new anti-cancer treatment, death, or withdrawal of consent until end of study. MRI/CT scans can be obtained earlier if clinical deterioration necessitates an earlier scan at the discretion of the managing physician. End of treatment CT/MRI should be performed only for subjects that discontinue treatment for a reason other than disease progression per **RECIST 1.1** criteria. Every assessment must include the chest, abdomen, pelvis, and all other known sites of disease. Tumor burden assessments will be performed based on **RECIST 1.1** guidelines ([Appendix D](#)). Radiographic response (CR and PR) requires confirmation by a repeat consecutive assessment 4 weeks after the first detection of response.

ⁱ All subjects with history of brain metastasis must have MRI of the brain performed within 28 days prior to enrollment. Only if MRI is contraindicated, then CT with contrast is acceptable. Subsequently, MRI brain scans can be performed at any time if clinically indicated or per standard of care. Any additional imaging used to evaluate or determine response (eg, PET, CT/PET, bone scan, etc) should be sent along with the required imaging to the central imaging vendor promptly upon completion.

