7.5 Radiological Imaging Assessment

The extent of disease will be evaluated by contrast-enhanced MRI/CT according to **RECIST 1.1** ([Appendix D](#)). All radiological imaging will be performed as indicated in the Site Imaging Manual provided by the central imaging core laboratory. In order to reduce radiation exposure for subjects, low dose CT should be utilized whenever possible.

The screening scans must be performed within 28 days prior to enrollment and will be used as baseline. All subsequent scans will be performed in the same manner as at screening, with the same contrast, preferably on the same scanner. Radiological assessment must include MRI/CT of the chest, abdomen and pelvis, as well as assessment of all other known sites of disease as detailed within the Site Imaging Manual. Magnetic resonance imaging (MRI) of the brain should be performed if signs or symptoms suggestive of central nervous system metastases are present.

The same imaging modality, MRI field strength and intravenous and oral contrast agents should be used at screening should be used for all subsequent assessments. Liver specific MRI contrast agents should not be used. To reduce potential safety concerns,

macrocyclic gadolinium contrast agents are recommended per National Health Institute guidelines, or follow local standards if more rigorous.

During treatment and follow-up radiological imaging of the chest, abdomen, pelvis, as well as all other known sites of disease, will be performed independent of treatment cycle every 6 ± 1 weeks for the first 4 response assessments. After **four** 6-week response assessments, radiological imaging and tumor assessment will be performed every 12 ± 1 weeks. Radiologic imaging and tumor assessment will be performed until disease progression, start of new anticancer treatment, death, withdrawal of consent or until end of study. Imaging may also be performed more frequently if clinically necessitated at the discretion of the managing physician. Radiographic response (complete response, partial response) requires confirmation by a repeat, consecutive scan at least 4 weeks after the first documentation of response and may be delayed until the next scheduled scan to avoid unnecessary procedures.

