All subjects with brain metastasis must have MRI of the brain performed within 28 days prior to first dose of AMG 510. Subsequently, brain scans may be performed at any time if, in the judgement of the managing physician. All brain scans on protocol are required to be MRI unless MRI is contraindicated, and then CT with contrast is acceptable.

Radiological imaging assessment during the EOT visit should be performed only for subjects that discontinue treatment for a reason other than disease progression per **RECIST 1.1** guidelines.

Determination of disease response for clinical management of subjects will be assessed at the clinical sites per **RECIST 1.1**. Scans will be submitted to a central imaging core laboratory for archival, response assessment including **RECIST 1.1**, and/or exploratory analysis eg, volumetric and viable tumor measurements. Detailed information regarding submission of images to the central imaging core laboratory is found in the Site Imaging Manual.

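### Two incompatible scan calendars apply to subjects who stop AMG 510 without progression before about week 24; sites using the 12-weekly one will find progression later in those subjects

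*Supplement*

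**What the plan says.** The texts are protocol Amendment 3 and SAP Amendment 1.

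**Imaging rule.** Section 7.5 opens "During treatment and follow-up radiological imaging of the chest, abdomen, pelvis" and says that imaging "will be performed independent of treatment cycle every 6 ± 1 weeks for the first 4 response assessments". After that, "radiological imaging and tumor assessment will be performed every 12 ± 1 weeks". The end of scanning is defined by "Radiologic imaging and tumor assessment will be performed until disease progression, start of new anticancer treatment, death, withdrawal of consent" or end of study. End of treatment is not on that list. Footnote i of Table 2 and footnote h of Table 6 repeat the rule: "Radiological imaging and tumor assessments are required at screening and every 6 ± 1 weeks", moving to 12 ± 1 weeks after four assessments.

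**Follow-up rule.** Section 7.2.5, footnote j of Table 2, footnote q of Table 6 and the long-term follow-up definition in SAP Section 5 cover subjects who stop treatment without confirmed progression or new therapy. For them, "tumor assessments will continue during LTFU every 12 weeks", with a window of ± 2 weeks. The period follows the safety follow-up visit, but no date is given from which the 12 weeks run.

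**Scans around stopping.** "Radiological imaging assessment during the EOT visit should be performed only for subjects that discontinue treatment for a reason other than disease progression", and "the EOT visit should occur as soon as possible (within 14 days) after the last dose of investigational product". In the copy available, Table 6 also marks a scan at the safety follow-up visit (about 30 days after last dose), which Section 7.5 does not mention.

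**Analysis.** The PFS rate at 6 and 12 months is a phase 2 secondary endpoint. SAP Table 1 dates progression at first observation and has no rule for long gaps between scans. SAP Table 9 lists no PFS sensitivity analysis.

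**The concern.** Tables 2 and 6 each carry both rules, so two sites can both follow the protocol and scan the same kind of subject on different dates. Progression is dated at the scan that shows it, so a sparser calendar moves the event later.

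Under Section 7.2.5, how soon progression is found before week 24 depends on whether the subject is still taking the drug. Subjects who stop for intolerance would then appear progression-free for longer than similar subjects who stay on treatment. The 6-month PFS rate is read just after the window in which the rules differ. DOR ends on the same progression date, so it is open to the same effect, although that was not computed.

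**Working it through.** **No figure to reproduce.** The documents give no assumed PFS rate, PFS power or rate of stopping without progression.

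**One subject, last dose at week 15**
- End-of-treatment scan at about week 16 under either rule.
- Section 7.5, counted from cycle 1 day 1: next scans at weeks 18 and 24.
- Section 7.2.5: 15 + 1 + 12 = week 28 if the clock runs from the end-of-treatment scan, or 15 + 4.3 + 12 = week 31.3 if it runs from the safety visit.
- If the Table 6 safety-visit scan is done, it adds one at about week 19.3.
- A progression at week 22 is an event by week 24 under Section 7.5. Under Section 7.2.5 it is not seen until after 6 months (26.1 weeks), with or without the safety-visit scan.

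**Simulation inputs** (400,000 subjects per scenario)
- Median PFS 2.8 and 5.4 months: the ends of the range quoted for other NSCLC therapies in protocol Section 2.2.1, used only for scale. A 7.0-month median is an added assumption. None is an AMG 510 assumption from the plan.
- Stopping by week 24 if progression did not intervene, p = 5%, 10% or 20% (assumed).
- 15% of PFS events are deaths, dated exactly (assumed).
- End-of-treatment scan 1 week after last dose under both rules.
- 12-week clock from that scan (EOT) or from the safety visit at last dose + 4.3 weeks (SFU). No safety-visit scan is included.

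**Formulas.** Time to progression or death is exponential with rate λ = ln 2 / (median × 4.348) per week. The stopping hazard is h = −ln(1 − p)/24. Progression is dated at the next scan. Kaplan-Meier PFS is read at 26.1 weeks under each calendar.

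Check of the true rate: 0.5^(26.09/(5.4 × 4.348)) = 0.5^1.111 = 46.3%, which agrees with the simulated 46.2% to 46.3%.

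**Selected results** (differences taken before rounding)

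| Median PFS (months) | p | Clock | Cohort 6-month PFS, 7.5 vs 7.2.5 | Difference (points) | Early discontinuers, 7.5 vs 7.2.5 | Mean extra delay (weeks) |
|---|---|---|---|---|---|---|
| 2.8 | 5% | SFU | 25.0% vs 25.4% | 0.38 | 46.6% vs 60.7% | 6.1 |
| 2.8 | 20% | SFU | 25.1% vs 26.6% | 1.52 | 45.1% vs 58.7% | 6.0 |
| 5.4 | 10% | EOT | 48.7% vs 49.2% | 0.54 | 67.2% vs 74.7% | 4.0 |
| 5.4 | 10% | SFU | 48.7% vs 49.4% | 0.66 | 67.5% vs 76.7% | 5.8 |
| 7.0 | 5% | EOT | 57.5% vs 57.7% | 0.25 | 74.1% vs 80.6% | 4.0 |
| 7.0 | 10% | EOT | 57.5% vs 58.0% | 0.47 | 74.5% vs 80.6% | 4.0 |

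Early discontinuers are subjects who stop before both progression and week 24. The delay is averaged over those with a non-fatal progression before week 24.

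Across all 18 scenarios the cohort difference is 0.25 to 1.5 points, the difference in early discontinuers is about 6 to 14 points, and the mean extra delay is about 4 to 6 weeks.

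**Cross-check.** With median 5.4 months, p = 10% and the EOT clock, 7.2% of subjects stop before both progression and week 24. Then 0.072 × (74.7 − 67.2) = 0.54 points, as simulated.

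**Sampling error.** With 105 subjects and a rate of 48.7%, √(0.487 × 0.513/105) = 0.049, or about 5 points.

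**The case against.** **The follow-up rule may be a deliberate exception.** Footnote q is the more specific text for subjects off treatment, so it could be meant to override footnote h. That reading is possible, but nothing states it. Section 7.5 names follow-up in its scope and does not stop at end of treatment. If the exception is intended, the sparser scanning of discontinuers before week 24 is intended too, and the start of its clock is still missing.

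**The bias is conditional.** A reader might infer that 6-month PFS is inflated as planned. The documents do not support that. Later detection arises only where sites follow Section 7.2.5, and only before about week 24. After that both rules give 12 weeks and differ only in the window.

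**The size depends on details the plan leaves open.** A reader might put the cohort effect at 1.5 to 3 points. That range comes from a narrower model: stopping between weeks 7 and 18, median 12 to 26 weeks from then to progression, 10% of subjects affected, clock from the safety visit, and no scan at that visit. The subset's 6-month PFS is then 80% to 89% against 52% to 74%, so 0.10 × (89 − 74) = 1.5 and 0.10 × (80 − 52) = 2.8 points. With the scan that Table 6 marks, it is 68% to 83%, giving 0.9 to 1.6 points. Running the clock from the end-of-treatment scan as well gives 61% to 79%, or 0.5 to 0.9 points. The larger range therefore omits a marked scan and relies on a start date the plan does not give.

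**Other limits stand.** Earlier scans are allowed on clinical deterioration. New anticancer therapy ends scanning under both rules and was not modeled. The only discontinuations reported in protocol Section 2.6.2.1 are 4 of 22 subjects, all for progression. Follow-up was short, so this neither supports nor excludes the assumed stopping rates.

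**The primary endpoint.** A reader might infer that ORR suffers, because a partial response found just before stopping could wait for its confirming scan and be lost to regrowth. No such effect has been computed. Confirmation has its own 4-week requirement. Section 7.5 permits waiting for the next scheduled scan but does not require it. The end-of-treatment and safety-visit scans limit any gap, and any loss would lower ORR.

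**Conclusion.** The contradiction is real in the current protocol, and the SAP repeats only the 12-weekly rule. It affects subjects who stop without progression before about week 24. Where Section 7.2.5 is followed, their progressions are found about 4 to 6 weeks later on average and their 6-month PFS is about 6 to 14 points higher. The reported cohort rate rises by about 0.25 to 1.5 points, well inside sampling error. The safety-visit scan, if done, would reduce these figures.

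The direction follows from the texts. The sizes rest on assumed stopping rates of 5% to 20%, a 15% death share, exponential times, the chosen medians and an assumed start for the clock. The documents support neither a certain inflation of PFS nor any stated effect on ORR. The case for acting is that the dates of scans for a named secondary endpoint are ambiguous, depend on treatment status under one reading, and cannot be recovered after data collection.

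**What to change.** Reconcile Section 7.2.5, Table 2 footnote j, Table 6 footnote q and the long-term follow-up definition in SAP Section 5 with Section 7.5. One tumor-assessment calendar, counted from cycle 1 day 1, should apply on and off treatment until progression or new therapy: 6 ± 1 weeks for the first four assessments, then 12 ± 1 weeks. Keep the 12-weekly interval for telephone survival contacts. State in Section 7.5 whether the safety-visit scan marked in Table 6 is required, or remove the mark.

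The cost is wording in those places, plus about one to three scans per subject in the minority who stop before week 24 without progression. Section 7.5 already requires those scans. If some have already been taken 12-weekly, a PFS sensitivity analysis that allows for unequal scan intervals (for example, interval-censored) is the fallback.

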7.2.6 End of Study Visit

End of study is defined as the date of the final study visit (eg, LTFU) when assessments and/or procedures are performed.

7.2.7 Demographics

Demographic data collection including sex, age, race, and/or ethnicity will be collected in order to study their possible association with subject safety and treatment effectiveness.

Approved

7.2.8 Physical Examination

Physical examination will be performed as per standard of care. Physical examination findings should be recorded on the appropriate CRF (eg, medical history, event).

7.2.9 Physical Measurements

Height (in centimeters) should be measured without shoes. Weight (in kilograms) should be measured without shoes.

7.2.10 Performance Status

The subject's performance status will be assessed using the ECOG PS.

7.2.11 Pharmacokinetic Blood Sampling

For PK assessment, blood samples for quantitative determination of AMG 510 will be collected at time points specified in the Schedule of Assessments ([Section 7.1](#)). Sample collection, processing, storage, and shipping instructions are provided in a separate laboratory manual. For phase 2, intense PK collection will be performed at select sites in up to approximately 30 subjects at time points described for Group A. Sparse PK collection will be performed in the remaining subjects at time points described for Group B.

7.2.12 Urine Collection For Food Effect Assessment

On day 1 of the cycle in which the food effect assessment is conducted, urine will be collected **to measure active metabolites of AMG 510** for the following time periods: (1) 0 to 6 hours postdose, and (2) 6 to 24 hours postdose.

7.2.13 High-fat Meal

For the food effect assessment, the clinical site will provide standardized high-fat meal as described in the Schedule of Assessment ([Table 3](#)). A standard high-fat meal (approximately 50% of the total caloric content of the meal) and high calorie (approximately 800 to 1000 calories) meal will be used as a test meal. The test meal should derive approximately 150, 250 and 500 to 600 calories from protein, carbohydrate and fat, respectively. An example test meal would be 2 eggs fried in butter, 2 strips of bacon, 2 slices of toast with butter, 4 ounces (approximately 120 mL) of hash brown potatoes, and 8 ounces (approximately 240 mL) of whole milk. Substitutions in this meal can be made as long as the meal provides a similar amount of calories from protein, carbohydrate, and fat and has comparable meal volume and viscosity. Further details of the high fat meal will be recorded in subject medical record and eCRF.

Approved

7.2.14 Vital Signs

The following measurements must be performed: systolic/diastolic blood pressure, heart rate, respiratory rate, pulse oximetry, and temperature. Subject must be in a supine position in a rested and calm state for at least 5 minutes before blood pressure assessments are conducted. If the subject is unable to be in the supine position, the subject should be in most recumbent position as possible. The position selected for a subject should be the same that is used throughout the study and documented on the vital sign CRF. The temperature location selected for a subject should be the same that is used throughout the study and documented on the vital signs CRF. Record all measurements on the vital signs CRF.

7.2.15 Electrocardiograms (ECGs)

Subject must be in supine position in a rested and calm state for at least 10 minutes before ECG assessment is conducted. If the subject is unable to be in the supine position, the subject should be in most recumbent position as possible. ECGs should be performed in a standardized method, in triplicate, and run consecutively, prior to blood draws or other invasive procedures. Each ECG must include the following measurements: QRS, QT, QTc, RR, and PR intervals.

- ≥ 3 baseline ECGs collected **at least** ≥ 30 **seconds** apart, with each baseline ECG in triplicate run consecutively (ie, total ≥ 9 ECGs)
- Triplicate ECGs at time points after dosing

Baseline is defined as prior to dosing on cycle 1 day 1. The PI or central reader will review all ECGs. ECGs will be transferred electronically to an ECG central reader for analysis per Amgen instructions. Once signed, the original ECG tracing will be retained with the subject's source documents. At the request of the sponsor, a copy of the original ECG will be made available to Amgen. Standard ECG machines should be used for all study-related ECG requirements. In certain circumstances Amgen may be able to provide a standard ECG machine if a site is unable to provide one.

For phase 2, intense ECG collection will be performed at select sites in up to approximately 30 subjects at time points described for Group A. Sparse ECG collection will be performed in the remaining subjects at time points described for Group B.

7.3 Intensive Procedures

All subjects in phase 1 (dose exploration and dose expansion) will have intensive PK and ECG data collected. At select sites, up to a total of 30 phase 2 subjects will also be

Approved

consented to have intensive PK and ECG data collected. Please refer to [Table 5](#) and [Table 6](#) for timing of collection.

7.4 Clinical Laboratory Assessments

Refer to [Table 7](#) for the list of analytes to be performed and to the Schedule of Assessments ([Table 2](#), [Table 5](#), and [Table 6](#)) for the timing and frequency.

The investigator is responsible for reviewing laboratory test results and recording any clinically relevant changes occurring during the study in the Event CRF. The investigator must determine whether an abnormal value in an individual study subject represents a clinically significant change from the subject's baseline values. In general, abnormal laboratory findings without clinical significance (based on the investigator's judgment) are not to be recorded as adverse events. However, laboratory value changes that require treatment or adjustment in current therapy are considered adverse events. Where applicable, clinical sequelae (not the laboratory abnormality) are to be recorded as the adverse event.

All protocol-required laboratory assessments, as defined in [Table 7](#), must be conducted in accordance with the laboratory manual and the Schedule of Assessments ([Table 2](#), [Table 5](#), and [Table 6](#)).

7.5 Radiological Imaging Assessment

The extent of disease will be evaluated by contrast-enhanced MRI/CT according to **RECIST 1.1** ([Appendix D](#)). All radiological imaging will be performed as indicated in the Site Imaging Manual provided by the central imaging core laboratory. In order to reduce radiation exposure for subjects, low dose CT should be utilized whenever possible.

The screening scans must be performed within 28 days prior to enrollment and will be used as baseline. All subsequent scans will be performed in the same manner as at screening, with the same contrast, preferably on the same scanner. Radiological assessment must include MRI/CT of the chest, abdomen and pelvis, as well as assessment of all other known sites of disease as detailed within the Site Imaging Manual. Magnetic resonance imaging (MRI) of the brain should be performed if signs or symptoms suggestive of central nervous system metastases are present.

The same imaging modality, MRI field strength and intravenous and oral contrast agents should be used at screening should be used for all subsequent assessments. Liver specific MRI contrast agents should not be used. To reduce potential safety concerns,

macrocyclic gadolinium contrast agents are recommended per National Health Institute guidelines, or follow local standards if more rigorous.

During treatment and follow-up radiological imaging of the chest, abdomen, pelvis, as well as all other known sites of disease, will be performed independent of treatment cycle every 6 ± 1 weeks for the first 4 response assessments. After **four** 6-week response assessments, radiological imaging and tumor assessment will be performed every 12 ± 1 weeks. Radiologic imaging and tumor assessment will be performed until disease progression, start of new anticancer treatment, death, withdrawal of consent or until end of study. Imaging may also be performed more frequently if clinically necessitated at the discretion of the managing physician. Radiographic response (complete response, partial response) requires confirmation by a repeat, consecutive scan at least 4 weeks after the first documentation of response and may be delayed until the next scheduled scan to avoid unnecessary procedures.

All subjects with brain metastasis must have MRI of the brain performed within 28 days prior to first dose of AMG 510. Subsequently, brain scans may be performed at any time if, in the judgement of the managing physician. All brain scans on protocol are required to be MRI unless MRI is contraindicated, and then CT with contrast is acceptable.

Radiological imaging assessment during the EOT visit should be performed only for subjects that discontinue treatment for a reason other than disease progression per **RECIST 1.1** guidelines.

Determination of disease response for clinical management of subjects will be assessed at the clinical sites per **RECIST 1.1**. Scans will be submitted to a central imaging core laboratory for archival, response assessment including **RECIST 1.1**, and/or exploratory analysis eg, volumetric and viable tumor measurements. Detailed information regarding submission of images to the central imaging core laboratory is found in the Site Imaging Manual.

